### **15.0** Potential Benefits to Participants

15.1 Potential Benefits: There may or may not be benefits to receiving higher amounts of macronutrients during the first week of life. In a few small retrospective studies infants receiving higher amounts of nutrition in the first week of life had improved neurodevelopmental scores on standardized testing and improved growth, including improved head growth, increased amounts of lean mass and increased weight gain. Also, in a few small randomized trials infants had less hyperglycemia, and lower rates of cholestasis. Infants who are randomized to the enhanced nutrition protocol may experience these benefits.

#### 16.0 Data Management

15.1 Data Analysis Plan: Data from the various domains will be entered by the study personnel into a web-based secure database (RedCap) for storage, retrieval and analysis. The NICU dietician is responsible for abstracting nutritional data from the electronic medical record (Epic). ADP data will be entered into the database by the study coordinators. ERP data will be abstracted by [name] and cleaned of artifacts as previously described. The data analyst will examine each variable for outliers and distributional properties and flag and correct entry errors where possible

and will log-transform or otherwise normalize variables prior to analysis. From RedCap all datasets will then be securely stored using Box.com per the HRPP policy. They may need to be downloaded to University/AHC desktops for statistical analysis, however only a subset of the team will be given access to all files (study coordinator and PI) and the rest will have access to the de-identified files only. These laptops are password protected and maintained by the AHC. Although we do not anticipate many missing values in this short-term follow-up study, multiple imputation methods (e.g., Proc MI in SAS) will be used if missing data can reasonably be considered missing at random. Analyses will also be run without imputation and results compared. Analyses will be carried out using SAS version 9.4 (SAS Institute Inc.) using an intent-to-treat approach, with a 2tailed p<0.05 as the threshold for statistical significance. For Specific Aims 1, 2, and 3, body composition data, neurodevelopmental outcomes, and IGF-1 and IGFBP3 will be treated as continuously-distributed variables assessed at multiple time points. For the ERP outcomes (which are measured twice), the primary hypotheses will be addressed using a simple general linear regression model for term-equivalent measures, and another similar model for 4 month corrected age measures, with assigned group as the independent variable in both cases. For FFM (with up to 10 repeated measures) and IGF-1 models, mixed effects regression models (using

PROC MIXED) will be used. The primary models will test assigned group (standard versus enhanced nutrition protocol) and assigned group x time interaction as the tests of differences in the group mean values for initial levels, and change over time, respectively, between intervention and control groups. To improve the precision of estimates, variables of interest (e.g., gestational age at birth, anthropometric z scores at birth, degree of illness, etc.) will be included in additional, secondary models. In addition, in Specific Aim 3, IGF-1 levels at both 1 week and 35 weeks will be examined as predictors of later neurodevelopment and body composition outcomes. IGF-1 will be considered a potential mediator of the intervention-outcome relationships if 1) the intervention is significantly associated with both IGF-1 levels and outcomes, 2) IGF-1 levels are significantly associated with FFM and neurodevelopmental outcomes, and 3) in a model that includes both IGF-1 and treatment group as predictors. the effect of treatment group on outcomes (mean differences) is diminished compared to results from models unadjusted for IGF-1. Other ways of assessing the possible role of IGF-1 in the treatment-outcome relationship will also be explored.

15.2 Power Analysis: A sample size of 40 infants in each treatment group (80 total) allows for up to a ~12% loss to follow-up after discharge and still have 35 infants per group. Our prior work showed a significant association of early nutrition (protein and calories in first week of life) with FFM gains throughout hospitalization (p<0.01 for both) in 34 VLBW preterm

> infants. We have also shown that higher energy (kcal/kg/day) across hospitalization was associated with faster speed of processing (shorter latency) in 16 preterm subjects. We therefore expect that this pilot study, which is 2-3 times as large as previous studies, will be sufficient to produce statistically significant differences between groups. As this is a pilot trial, however, we have not conducted a formal power calculation. Rather, the results of this pilot exploratory study will generate estimates of effect size that will then be used to calculate sample size for our planned larger trial.

15.3 Data Integrity: Describe any procedures that will be used for quality control of collected data. All data will be stored in a RedCap database designed by the data manager for this study prior to data collection. All necessary medical record data (including the daily information on nutritional intake, procedures, and clinical outcomes, among others) will be abstracted by the clinical research manager on a weekly or biweekly basis. Body composition and ERP data will be exported in Excel format on a weekly or biweekly basis and shared on a password protected server with the data manager. While body composition data and ERP data go directly from Excel into RedCap, there is a possibility of data entry errors for the medical record data, and so the data manager or PI will conduct biweekly (initially) then monthly checks of data accuracy by comparing RedCap data against medical records data for validation in a subset of subjects. On a monthly basis, data quality will be examined for outliers and unusual values by the data manager, who will then communicate with the clinical research manager or other data collection personnel with access to the original data to resolve the errors and insure consistency in units and data collection processes.

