### 4.0 Study Intervention

4.1 Description: This nutritional intervention is designed to accelerate the addition of macronutrients over the first week of life to minimize the period of malnutrition, and is based upon the findings of numerous smaller, less comprehensive studies and expert opinion. Once consent is obtained, and the infant is admitted to the NICU, enrolled infants will be randomized to either receive parenteral nutrition per the standard NICU parenteral nutrition protocol or via the enhanced nutrition protocol for the first week of life via random envelope selection. Stratified

block randomization will be performed. Infants will be stratified by gestational age (22-25, 26-29, 30-32 weeks). Within each stratum, permuted block randomization will ensure that study personal are unable to predict treatment allocation. Infants

randomized to the enhanced nutrition protocol will receive starter total parenteral nutrition (TPN) initiated at 80 mls/kg/day to provide protein at 4 grams/kg/day and a glucose infusion rate (GIR) of ~5.5 mgs/kg/min as soon as IV access has been obtained. Enhanced nutrition protocol infants will also be started on intralipids (IL) at 2 grams/kg/day once IV access is obtained. Infants randomized to the enhanced nutrition protocol will receive 4 grams/kg/day of protein throughout the first week of life. IL will be increased to 3 grams/kg/day on day of life (DOL) 2 and to 3.5 grams/kg/day on DOL 3. They will remain on this amount for at least the first week of life or until sufficient enteral feeding volumes have been established. GIR will be advanced by  $\sim 1.5 \text{ mgs/kg/min per day}$ throughout the first week of life to a maximum of 12-14 mgs/kg/min. Again, they will then remain on this amount until sufficient enteral feedings have been established (typically approximately 1-2 weeks). Infants randomized to the standard nutrition protocol will receive macronutrients per the caregivers discretion, most commonly initiated with starter TPN at 60 mls/kg/day giving 3 grams/kg/day of protein and a GIR of ~4 and IL provided at 0-1 gram/kg/day. Advancement is most typically by 1

mg/kg/min per day for GIR and 1 gram/kg/day per day for IL and protein in the standard NICU protocol. Pertinent aspects of the differences in nutritional treatment in intervention and control groups are summarized in the table below

	Day 1	Day 2	Day 3	Day 4	Day 5	Day 6	Day 7	
Control								
GIR	4.2	5	6	7	8	9	10	

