Growth and Body Composition Measures (Outcomes for Aim 1): Daily weights will be measured per unit protocol on an electronic scale to the nearest 1 gram. Weekly recumbent length (using an infant length board) and head circumference (using a flexible tape measure) measurements will be performed by a consistent measurement team to the nearest 0.1cm throughout their hospitalization, as well as at the term and 4 mo CA follow-up visits. Once clinically stable and able to tolerate room air for >5minutes, we will begin measurements of body composition (FM, FFM and percent body fat) via infant ADP ("Pea Pod"; COSMED, INC, Concord, CA) by a trained NICU nurse, physician or research staff, and repeat these measurements weekly as tolerated. A detailed description of the Pea Pod's physical design, operating principles, validation and measurement procedures is provided elsewhere. Briefly, the Pea Pod (1-8kg) measure the infant's volume using air-displacement plethysmography, and then calculates the density using the infant's mass and length. FM and FFM are then calculated using Fomon's model. At a minimum, we plan to obtain one body composition measurement prior to discharge home from the NICU.

Families will be contacted monthly with study updates and general information on standard care of preterm infants following discharge to reduce loss to follow-up/maintain engagement in the study and will be scheduled for follow-up body composition and neurodevelopmental assessment at term (or as soon as possible post-discharge) and again at 4 months CA, when weight, recumbent length and head circumference will be measured, along with body composition using ADP. Raw body composition variables will be converted to z scores using our new preterm and term-corrected infant body composition reference data for ADP.

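### Randomisation is stratified by gestational age, but no named primary model includes the strata: adding them costs almost nothing and gains precision to the extent that gestational age predicts the outcome

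*Combined protocol and SAP*

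**What the plan says.** Section 4.1 fixes the design: "Infants will be stratified by gestational age (22-25, 26-29, 30-32 weeks"), with permuted blocks inside each stratum. The block size is not given.

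Section 16.0 (item numbered 15.1) sets out the primary models:

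- **ERP:** one linear regression at term and one at 4 months corrected age, "with assigned group as the independent variable in both cases".
- **FFM and IGF-1:** mixed models in which group and group by time serve as the "tests of differences in the group mean values for initial levels, and change over time, respectively".

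The same section justifies covariates in these words: "To improve the precision of estimates, variables of interest". It gives gestational age at birth, birth z scores and degree of illness as open-ended examples, and says that they "will be included in additional, secondary models".

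Item 15.2 plans 40 infants per group, which "allows for up to a ~12% loss to follow-up after discharge and still have 35 infants per group". It states that no formal power calculation was done and that the pilot is to "generate estimates of effect size that will then be used to calculate sample size for our planned larger trial". Section 3.1 makes first-week calorie and protein intake the primary outcome; section 16.0 names no model for it.

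**The concern.** Blocking within gestational-age strata makes the arms alike on gestational age. If gestational age is prognostic, this reduces the true sampling variance of the group difference. A group-only model leaves the between-stratum variance in its residual, so its standard error does not reflect that reduction. The estimate remains unbiased, but its interval is wider than the design warrants and the test rejects less often than its nominal level.

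The plan recognises that such covariates add precision, yet reserves them for secondary models whose covariate list is left open. A pilot meant to supply effect sizes for the next trial, with about 35 infants per arm, has little precision to spare.

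**Working it through.** **Inputs from the documents.** 40 per group, about 12% loss, 35 per group analysed, two-sided 5% (section 16.0); three strata, permuted blocks (section 4.1). The plan's figure reproduces: 40 × 0.88 = 35.2, and 35/0.88 = 39.8, rounded up to 40. No power, SD or effect size is stated.

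**Assumed.** R², the share of outcome variance explained by the strata, from 0 to 0.5. Differences are in units of the outcome SD.

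**1. Cost.** Two stratum indicators take the residual degrees of freedom from 70 − 2 = 68 to 70 − 4 = 66. The critical t goes from 1.9955 to 1.9966 (+0.05%). If R² = 0, the difference detectable with 80% power goes from 0.679 to 0.680 SD.

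**2. Gain at one time point.** The group-only model reports SE = √(2/35) = 0.239, so the 95% half-width is 1.9955 × 0.239 = 0.48 SD. With strata, SE = 0.239 × √(1 − R²):

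| R² | SE multiplier | 95% half-width | Detectable difference, 80% power |
|---|---|---|---|
| 0.1 | 0.949 | 0.45 | 0.645 |
| 0.3 | 0.837 | 0.40 | 0.569 |
| 0.5 | 0.707 | 0.34 | 0.481 |

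**3. Calibration under stratified blocks.** Simulation: 80 randomised, random loss to 70, three equal strata, blocks of 4, 8,000 trials per setting. Monte Carlo error is about 0.25 points for size, 0.6 for power and 0.8% for the SE ratio. Excess is reported SE over true SE.

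| R² | Group-only SE excess | Group-only size | Power at 0.5 SD, group-only | Power at 0.5 SD, with strata |
|---|---|---|---|---|
| 0 | about 0 (−1.6%, about 2 Monte Carlo SEs) | 5.2% | 54.9% | 54.3% |
| 0.05 | 1% | 5.0% | 54–55% | 56% |
| 0.1 | 5% | 3.8% | 54–55% | 57% |
| 0.2 | 10% | 3.3% | 54–55% | 63% |
| 0.3 | 17% | 2.5% | 54–55% | 69% |
| 0.5 | 31% | 1.1% | 54–55% | 82% |

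At R² = 0.3 the excess is 15–17% for blocks of 2, 4, 6 or 8, and 14% with strata of 20/50/30%. A second simulation (strata 20/45/35%) gave group-only sizes of 5.1, 4.2, 2.1 and 1.1% at R² = 0, 0.1, 0.3 and 0.5, against 5.3, 5.2, 4.3 and 4.9% with strata. At R² = 0.3 the group-only SE was reported as 0.239 when the true value was 0.203.

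**4. Dependence on the assumed effect.** At 0.5 SD the effect sits just above the group-only rejection limit of about 0.477, so group-only power stays near 54–55% whatever R² is. At 0.68 SD it rises too: 81, 83 and 87% group-only against 84, 92 and 97% with strata, for R² = 0.1, 0.3 and 0.5. The gains there are 3, 9 and 10 points.

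**5. Mixed models.** Assumed: 70 infants, 6 equally spaced visits, SDs of 1 (intercept), 0.15 per visit (slope) and 0.4 (residual); 6,000 trials per setting.

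- *Strata shift level only.* The group main-effect SE is reported as 0.249 against a true 0.216 (30% of level variance) or 0.194 (50%): 0.249/0.216 = 1.15 and 0.249/0.194 = 1.28. The group by time SE is 0.0424 without strata and 0.0425 with stratum by time, so nothing is gained.
- *Strata also explain 30% of slope variance.* The group by time SE is reported as 0.0424 against a true 0.0384 (size 3.0%). Stratum by time brings it to 0.0376.
- *Two visits, as for IGF-1.* Even then it moves only from 0.1394 to 0.1383. The variance of an infant's slope is 0.15² = 0.0225 plus residual 0.4²/0.5 = 0.32, and the residual dominates.

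**The case against.** The strongest reply is that nothing is lost: the adjusted analysis is already planned, and whoever designs the larger trial can take the adjusted estimate from the same report. That is largely true, and it is why this is not a validity problem. But the secondary covariate set is given only by example, so it could be settled after results are seen. The result labelled primary would still be the less precise one.

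Four further points stand as limits on the size:

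- **R² is unknown and may be low.** Section 5.2 says "Raw body composition variables will be converted to z scores", and ERP is tested at term and 4 months corrected age, so much of the gestational-age effect may already be removed. At R² of 0.05 the excess is about 1%, within simulation noise. The rows for 0.3 and 0.5 are illustrative.
- **Aim I concerns FFM gains, which is the group by time test.** A stratum main effect does nothing for it. The more direct benefit is in the two ERP models and the comparison of starting levels.
- **The mixed-model figures assume balanced visits.** Section 5.2 starts body-composition measurement only when an infant is stable, repeats it as tolerated and plans at least one measurement before discharge. Those standard errors show direction, not expected values.
- **ERP, FFM and IGF-1 are secondary outcomes.** The absence of a model for the primary outcome is a separate and larger gap. No gain has been estimated for intake.

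None of this reverses the balance: the possible loss from including the strata is under one power point.

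**Conclusion.** The concern holds. The named primary models omit the factor used to stratify randomisation. The result is inefficiency, not bias: the group-only test keeps its type I error at or below 5% and gives up precision only if gestational age predicts the outcome.

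For single-time-point comparisons with 35 per group, the reported standard error would be too large by about 5% if the strata explain 10% of variance and about 17% if they explain 30%. It would be right if they explain none. These figures rest on assumed R², random loss and assumed block and stratum sizes. The power gain also depends on the assumed effect: at R² of 0.3 it is about 14 points at 0.5 SD but about 9 at 0.68 SD. The group by time test benefits only if the strata predict slope and stratum by time is fitted. This is a low-cost improvement that should be made.

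**What to change.** In section 16.0:

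1. Include the three-level gestational-age stratum in the primary ERP, FFM and IGF-1 models, and in whatever model is specified for first-week energy and protein intake. Continuous gestational age at birth is an acceptable alternative, but one form should be named in advance.
2. Add stratum by time to the FFM mixed model if the change-over-time test is also to benefit.
3. Keep the group-only models as prespecified sensitivity analyses.
4. Treat birth z score as an optional further covariate. It is not part of the stratification argument.

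The cost is SAP wording and two degrees of freedom (four with stratum by time). Gestational age is known at randomisation and already collected, so no new data are needed.

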### 1.0 Objectives

1.1 The overall objective of the proposal is to demonstrate the feasibility of providing increased calories and protein in the first week of life to VLBW preterm infants, and to generate pilot data on the effects of this intervention on growth and neurodevelopmental outcomes. We hypothesize that infants receiving greater calories and protein in the first week of life will have improved FFM gains and higher levels of IGF-1 prior to discharge, and improved early cognition and faster speed of neural processing measured at term and 4 months corrected age (CA). To address these hypotheses, we propose the following specific aims:

Specific Aim I. Examine whether infants receiving earlier initiation of intralipids and more rapid increases in energy and protein intake during the first week of life ("enhanced nutrition protocol") have improved growth, indexed by increased FFM gains, compared to a standard nutrition protocol. Body composition will be measured weekly using air displacement plethysmography (ADP) until discharge and at term and 4 months CA.

Specific Aim II. Determine if infants on the "enhanced nutrition protocol" have improved cognition and faster speed of processing at term and 4 months CA compared to a standard nutrition protocol. Neurodevelopmental outcomes will be measured using electrophysiologic (ERP) techniques.

Specific Aim III. To assess whether growth factors, including IGF-1 and IGFBP3, mediate the relationship between improved nutritional provision and improved FFM gains, cognition, and speed of processing in preterm infants. Growth factors will be drawn at 1 week of age and 35 weeks PMA.

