Markers of Growth hormone axis activity (Outcomes for Aim 3): IGF-1 and IGFBP3 levels will be obtained in serum at 1 week of age and ~35 weeks CA. These specific markers were chosen as associations have been seen between linear growth, FFM gains, metabolic risk (e.g. increased adiposity and higher blood pressure), neurodevelopmental outcomes and IGF-1 and IGFBP3 in preterm born infants . IGF-1 and IGFBP3 will be analyzed by the Fairview Clinical Laboratory.

Additional Measures: The randomized design of this trial is expected to make the distribution of potential confounder values and characteristics similar in the intervention and control groups. Nonetheless, to confirm their equivalence and to describe the study sample, we will obtain birth anthropometrics, maternal age, education, and ethnicity, infant sex, gestational age at birth, weight-for-age z score at birth, and degree of illness from the medical record or parental self-report at enrollment. Degree of illness will be assessed using the Score for Neonatal Acute Physiology (SNAP) on DOL#1, 7, 14 and  $21^{34-35}$ . We will also collect data on other non-specific markers of illness, including days on the ventilator, requirement for blood pressure support, sepsis evaluations and antibiotic therapy, steroid administration, necrotizing enterocolitis (NEC), diagnosis of chronic lung disease and retinopathy of prematurity (ROP) etc. These measures will also allow us to track the safety of the intervention to ensure that rates of these common morbidities are similar in both groups.

5.3 Storage and Access: The records of this study will be kept private. In any publications or presentations, we will not include any information that will make it possible to identify the mother or baby as a subject. Any hard copies of the baby's research records will be kept in a locked desk in the locked office of the PI, co-I or study coordinator, and will be identified ONLY by an assigned study ID number (other identifying information will be removed). The study information will not be recorded in the medical record. These de-identified data will be entered into electronic format for storage and analysis; only the PI, co-Is, study coordinators and data analyst will have access to this electronic dataset.

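### The FFM and IGF-1 models label a post-treatment group difference as the initial level, so group x time leaves out any benefit already present at the first measurement

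*Combined protocol and SAP*

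**What the plan says.** Section 16.0, item 15.1, names the method: "For FFM (with up to 10 repeated measures) and IGF-1 models, mixed effects regression models". The primary models test assigned group and "assigned group x time interaction as the tests of differences in the group mean values for initial levels, and change over time, respectively". Gestational age, birth anthropometric z scores and illness enter only additional, secondary models. The text does not say whether time is age since birth or postmenstrual age, whether it is linear or categorical, or where zero lies.

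Section 1.0 frames Aim I as "improved growth, indexed by increased FFM gains, compared to a standard nutrition protocol". The hypothesis is that enhanced-protocol infants "will have improved FFM gains and higher levels of IGF-1 prior to discharge".

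On timing, Section 4.0 starts the enhanced protocol "as soon as IV access has been obtained". Section 5.2 says of air displacement plethysmography (ADP): "Once clinically stable and able to tolerate room air for >5minutes, we will begin measurements of body composition". The device range is given as 1-8 kg, and the planned minimum is one ADP before discharge. For growth factors, "IGF-1 and IGFBP3 levels will be obtained in serum at 1 week of age", and again at about 35 weeks.

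**The concern.** The labels suit a trial with a baseline measurement, where the intercept difference is chance and the difference in change is the effect. Here nothing is measured before treatment starts. A group difference at the first ADP, or in the 1-week IGF-1, is itself an effect of treatment. FFM gained before the first ADP, which includes much of the period when the intervention acts, cannot appear in the slope. The age at first ADP also depends on how stable the infant is after randomisation.

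Of the two labelled terms, only change over time corresponds to FFM gains. If that term is read as the Aim I test, a real early benefit may go unreported as such, or a fading benefit may be reported as slower growth. The mismatch is plainest for IGF-1: the hypothesis concerns a level, while group x time compares the change from 1 week to 35 weeks.

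The pilot's effect sizes are meant to size a larger trial, and the Aim III mediation rule requires a significant association of the intervention with IGF-1 and with the outcomes. Neither passage says which model term supplies these.

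**Working it through.** **The plan's own figure.** 40 per group allows about 12% loss: 35/(1 - 0.12) = 39.8, rounded up to 40. It reproduces. No effect size, SD or power is stated, so everything below except the zero-slope result rests on assumptions.

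**A benefit already present and kept.** If the group difference equals a constant d at every visit, the expected group x time coefficient is d - d = 0, whatever the variances. The test then rejects at its two-sided 0.05 level, 2.5% in each direction.

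**Other shapes for FFM.** Assumed: effect d = 0.7 SD; 35 per arm; first ADP at weeks 3-7, weekly to week 10, then term (week 12) and 4 months corrected age (week 29.4); infant SD 0.8; residual SD 0.5; slope SD 0.015 to 0.06 per week; linear time. Fading or growth is linear from week 3, over 29.4 - 3 = 26.4 weeks.

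With V = Z diag(0.8², slope SD²) Z' + 0.5² I, the variance of the group coefficients is (2/35) times the inverse of the average X'V⁻¹X. This gives a slope-difference SE of 0.0068 (slope SD 0.015) to 0.0155 (slope SD 0.06). The chance of a significant slope in the direction of the true slope difference is Φ(|difference|/SE - 1.96).

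- Half fades: -0.35/26.4 = -0.0133 per week. 0.0133/0.0068 = 1.96, giving 50%; 0.0133/0.0155 = 0.86, giving 14%.
- All fades: -0.70/26.4 = -0.0265. 0.0265/0.0068 = 3.90, giving 97%; 0.0265/0.0155 = 1.71, giving 40%.

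A second run of the same cases agrees within about two percentage points. Its ranges are tabulated and used elsewhere.

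| Shape of the 0.7 SD benefit | Slope favours enhanced | Slope favours control |
|---|---|---|
| Present at first ADP, kept | 2.5% | 2.5% |
| Half fades by 4 months | about 0 | 13-48% |
| All fades by 4 months | about 0 | 41-99% |
| Grows from zero to term, then flat | 25-83% | about 0 |
| Grows from zero to 4 months | 41-97% | about 0 |

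In the first row the group term, with time zero at week 3, has about 93-95% power.

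**Sensitivity to the visit window.** Using in-hospital visits only (weeks 3-9, effect 0.67 SD, intercept SD 0.9, residual SD 0.35, slope SD 0.03-0.06), half fading by the last visit gives -0.335/6 = -0.056 per week. The slope then favours control in 74-90% of trials.

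**A term contrast alone.** If the benefit grows to 4 months, the difference at term is 0.7 x 9/26.4 = 0.24. The SD at term is √(0.64 + 0.25 + 81 x slope SD²) = 0.95 to 1.09, and the SE is that times √(2/35) = 0.239, or 0.228 to 0.260. Power is about 15-18%, against 41-97% for the slope.

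**IGF-1, two draws.** In SD units, with correlation r between draws, the SE of the difference in change is √(2(2 - 2r)/35): 0.283 at r = 0.3 and 0.185 at r = 0.7. Take 0.67 SD, the difference with 80% power at one draw (0.67/0.239 = 2.80; Φ(2.80 - 1.96) = 80%).

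- 0.67 at both draws: expected interaction 0, rejection 5%; each single-draw contrast has 80%.
- 0.67 falling to 0.33: -0.34/0.283 = -1.20, giving 22% favouring control; -0.34/0.185 = -1.84, giving 45%.

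**The case against.** The strongest reply is that the primary models test two terms. An early, lasting benefit falls on the group term, which has high power if time zero is near the first ADP. That stands, so a reader who infers that the plan cannot see an early benefit goes too far. Nothing in the documents says a group difference would be dismissed as baseline imbalance either; that is only what the label invites. What remains is that the plan does not call this term a treatment effect. If time zero is birth, the term is also an extrapolation to before any ADP.

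Second, the slope is the right test for a benefit that builds up. The power section cites earlier work linking first-week nutrition to FFM gains throughout hospitalisation, which fits that shape. This also stands, and it rules out simply replacing the slope with a term contrast.

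Third, the reversal figures depend on assumed variances and fading curves. If controls do catch up, a slope favouring them correctly describes change; it misleads only if the group term is ignored. It is also tempting to say the 4-month visit dominates a linear slope, but the plan never says time is linear.

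Fourth, it would be inexact to say that all measurements follow the completed intervention. The 1-week IGF-1, and an early ADP in a stable infant above 1 kg, could fall during it. They follow its start, which is enough to rule out a baseline.

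**Conclusion.** The point holds as a mislabelled and under-specified analysis. Two parts need no assumed variances: no FFM or IGF-1 value precedes treatment, and group x time has only 5% rejection for a benefit that is present at the first measurement and constant afterwards. The mismatch with the IGF-1 hypothesis follows from the text alone.

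The reversal risk is real but its size is uncertain, as the width of the tabulated ranges shows. The documents do not support a claim that the slope test will usually reverse a benefit, or that it is useless.

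FFM and IGF-1 are secondary outcomes of a pilot. The primary outcome, calories and protein received in the first week, is untouched. The exposure is in the Aim I and Aim III conclusions and the effect sizes carried into the larger trial.

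**What to change.** In Section 16.0, item 15.1:

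- Define time as postmenstrual age, by visit category or spline, with a stated time zero. State that a group difference at any visit is a treatment effect, not a baseline difference.
- For FFM z score, pre-specify from the same PROC MIXED model either a joint test of group and group x time (2 df if time is linear, more with categories or a spline), or group contrasts at both term and 4 months corrected age, the time points the ERP models already use. If both contrasts serve as tests, say how the 0.05 is shared. Report the contrasts with confidence intervals for sizing the larger trial. Do not rely on the term contrast alone.
- For IGF-1, test the group difference at 1 week and at 35 weeks.
- Put the gestational-age stratum and birth size z score in the primary model. Keep group x time as a description of trajectory.

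No new data are needed. The cost is some power when the effect grows linearly. With 0.67 SD growing to 4 months, and the intercept, residual and slope SDs of the sensitivity check above, the joint test has 34-84% against 41-89% for the slope. For a benefit present early and kept, the joint test has about 81% against 5%.
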